# Rational to Study Timing of Radiation

Early palliative care has been shown to improve the quality of life and even survival for patients with metastatic cancer. More and more supportive oncology teams in cancer centers now advocate for early integration of radiation therapy in a patient's palliative management course. While multiple randomized studies have evaluated the efficacy of different radiation therapy regimens in the treatment of symptomatic bone lesions, there has not been a study that examined the impact of early, upfront radiation for asymptomatic or minimally symptomatic (non-opioid dependent) bone metastases and its efficacy in preventing SREs.

To better understand the pattern of inpatient radiation oncology care, an institutional inpatient radiation oncology consult registry was created which demonstrated that 319 of the 1,151 inpatient consults requested between July 2015 and June 2016 were for evaluation of symptomatic bone metastases in patients who were hospitalized for acute or chronic pain. Among these patients, two-thirds went on to receive RT for pain management. The most common sites treated with RT were spine (50%), joints such as hip and shoulder (11%), and long bones such as femur and humerus (11%). The median survival of all patients who were evaluated was 4 months, and 9% percent of patients discontinued RT to transition to hospice care, 8% died before the end of planned RT. Our data showed that in this selected patient population admitted for pain management of bone metastases, the overall prognosis is poor. Nevertheless, 61% of treated painful bone metastases were diagnosed at >4 months prior to RT. While RT is an effective treatment modality for palliation, it does appear RT may be delivered too late. The proposed trial seeks to understand whether it is beneficial to patients with metastatic disease to change the treatment paradigm to one of early, upfront RT prior to the development of symptomatic disease.

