## 4.2 Intervention

#### 4.2.1 Standard of Care

Patients randomized to Arm 1 will undergo appropriate therapy as determined by their oncologist. These patients will either continue their current therapy or be transitioned to a new standard of care therapy at the discretion of the treating oncologist. If randomized to Arm 1, these patients may undergo palliative RT for progressive, painful lesions (a skeletal related event) at time of symptom development (not upfront palliative RT).

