# 11.0 TOXICITIES/SIDE EFFECTS

The National Cancer Institute (NCI) Common Terminology Criteria for Adverse Events (CTCAE) version 4.0 will be used to evaluate toxicities. Adverse events will depend on the sites receiving RT and the normal tissues adjacent to those sites.

All patients undergoing RT are likely to experience fatigue within the first several months of treatment. RT toxicities will depend on the region treated as well as the regimen. If surgery is needed on the radiated bone, patient can also be at higher risk for infection. Additional possible toxicities associated with RT include and not limited to, by site:

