# 12.2 Secondary Outcome Measurements

Patients on both arms will be followed for accumulation of surrogates of health care cost, including number and duration of hospitalizations for SREs.

All study participants will be assessed for health related quality of life, measured using the BPI questionnaires, and health utilities using the EQ-5D-5L form.

Patients enrolled on both arms of the study will also be included in an analysis of pain-free survival, defined as time from study entry to start of opioids or death. Patients enrolled on both arms of the study will also be included in an analysis of overall survival, defined as time from study entry to death.

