## 14.0 BIOSTATISTICS

The primary objective of this study is to compare the rate of skeletal related events (SRE) from the date of randomization to death or 12 months, whichever occurs first, between patients who received standard of care versus upfront, early palliative RT to high-risk bone metastases. We expect 60-80% of the enrolled patients can be followed for 1 year. An SRE is defined as pathological fractures, spinal cord compression, or palliative radiotherapy and orthopedic surgery for bone pain. Data suggest that the event rate is around 60% in the standard of care arm . In our institutional experience, 75% of inpatient radiation consultation led to palliative radiation for painful bone

metastasis, an SRE. Furthermore, 61% of these lesions were diagnosed at least 4 months prior to undergoing RT. We believe 60% estimated event rate at 1-year is a conservative estimate.

The primary endpoint is a binary variable and the rate refers to proportion and is defined as the number of lesions that had SRE divided by the total number of target lesions. This analysis is lesion-based so an SRE (or no SRE) at one site does not affect the status of other sites from the same patient. We estimate that the investigational arm has the event rate around 30%. Radiation therapy is extremely effective in alleviating pain due to bone metastases with 70-80% pain control. By preventing the development of significant bone pain, which often leads to SREs, RT can effectively reduce SREs, To this end we will analyze at least 66 patients with valid SRE endpoint (randomized 1:1 to each arm) to achieve >80% power in detecting such a difference using a two-sample, one-sided proportion test with alpha<0.05. Since patients who withdraw before the endpoint can be evaluated will not be included in the analysis (i.e., it will NOT be an intent-to-treat analysis) we will over-accrue to account for withdrawals to ensure a minimum of 33 patients in each arm (subject to stratification, see Section 15.2) who can contribute the analyzable endpoint of SRE. We believe an additional 10% would be sufficient so totally we expect to randomize 74 patients. A small portion of patients (<15%) may have multiple lesions, in which case they will be treated as independent analysis units. In other words, the eventual effect sample size may be slightly higher than 66 because this objective will be analyzed per lesion.

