Palliative radiation therapy is a well-established, frequently used treatment for patients with metastatic disease. It is often the standard of care for patients with symptomatic metastatic lesion. It is extremely unlikely to be more toxic or cause earlier deaths.

We expect to enroll all 74 patients within 2 years.

Secondary objectives will be analyzed per patient. Unless otherwise specified, all endpoints are defined within the time window from the date of randomization to death or 12 months, whichever occurs first.

To compare the number of hospitalizations related to SREs between standard of care and upfront, early palliative RT arms we will employ a Wilcoxon rank sum test.

To compare quality of life between standard of care and RT arms, using the Brief Pain Inventory (BPI) and EuroQol Group EQ-5D-5L forms, we will test the difference (between the two arms) of the survey results at the following time points: 3 months, 6 months, 12 months and optionally but recommended within one week of any SRE. The individual quantitative scores derived from the BPI, and the utility scores as well as the overall health scores derived from EQ-5D-5L, will be summarized at these assessment times using descriptive statistics (means and standard deviations, medians and quartiles). Differences between the two arms in terms of these quantitative scores at various time points of interest will be evaluated for both statistical and clinical significance using Wilcoxon rank

Page **22** of **30** Version: 2/26/16

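### The only hospitalization comparison leaves out admissions caused by upfront RT, and no arm-neutral admission count is planned beside it

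*Combined protocol and SAP*

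**What the plan says.** The hospitalization objective is stated in Section 14.0 as "To compare the number of hospitalizations related to SREs between standard of care and upfront, early palliative RT arms", and the method follows at once: "early palliative RT arms we will employ a Wilcoxon rank sum test". No alpha, sidedness, power or expected rate is given for this test. Section 12.2 presents the count as a surrogate of cost, "including number and duration of hospitalizations for SREs", followed in both arms; Section 14.0 plans a test for the number only.

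Section 14.0 gives one SRE definition for both arms: "An SRE is defined as pathological fractures, spinal cord compression, or palliative radiotherapy and orthopedic surgery for bone pain". Section 4.2.1 says of Arm 1 that "these patients may undergo palliative RT for progressive, painful lesions (a skeletal related event) at time of symptom development (not upfront palliative RT". RT given on demand is thus named as an SRE and set apart from upfront RT. No section says outright that the planned Arm 2 course is not an SRE, but the design makes no sense otherwise.

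Section 10.0 restricts evaluation of RT-related adverse events to Arm 2, and Section 14.0 tabulates toxicity for that arm descriptively. Section 15.2 has physicians told the allocated arm. No section defines what makes an admission related to an SRE, and none plans an all-cause or RT-related admission comparison.

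**The concern.** Upfront RT can itself put patients in hospital. Section 11.0 lists pneumonitis, gastrointestinal bleeding, obstruction and perforation, and pain flare among its possible effects. When such an admission follows upfront RT, there is no SRE for it to be related to, so it drops out of the count. When the same complication follows on-demand palliative RT in Arm 1, the RT is an SRE and the admission can be attributed to it. Whether one kind of admission is counted may then depend on the arm, and the judgement is made by staff who know the arm.

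Two things are at stake. The comparison probably leans towards upfront RT. And a count offered as a cost surrogate omits both the admissions that the intervention can cause and the upfront RT courses themselves.

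**Working it through.** **Which admissions count.** Taking the definitions in Sections 4.2.1, 12.2 and 14.0 together:

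| Reason for admission | Arm 1 | Arm 2 |
|---|---|---|
| Fracture, cord compression, or pain leading to palliative RT or surgery | counted | counted |
| Bone pain managed without any SRE | not counted | not counted |
| Complication of orthopedic surgery to bone | attributable to an SRE | attributable to an SRE |
| Complication of on-demand palliative RT | attributable to an SRE, though the text does not fix it | same |
| Complication of upfront RT | does not arise | no SRE to attach to |

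Only the last row separates the arms.

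**The plan's own figure.** There is none for hospitalization. The primary sample size reproduces: with 60% v 30%, one-sided 0.05, 80% power and pooled variance, n = [1.645√(2×0.45×0.55) + 0.842√(0.24+0.21)]² / 0.30² = 32.9, so 33 per arm and 66 in all; 66/0.90 = 73.3, so 74. This point does not affect it.

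**Expected SRE-related admissions.** Inputs: 60% and 30% (Section 14.0), 25% of SREs admitted (Section 3.0, Hospitalization), 74/2 = 37 per arm. Assumption: one SRE per affected patient. The 60% and 30% are defined per lesion and are used here as per-patient rates, which is an approximation.

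- Arm 1: 0.60 × 0.25 = 0.150 per patient; × 37 = 5.55.
- Arm 2: 0.30 × 0.25 = 0.075 per patient; × 37 = 2.78.
- Difference: 5.55 − 2.78 ≈ 2.8 admissions; ratio 0.50.
- With the 26% from the other study cited in Section 3.0: 0.30 × 0.26 × 37 = 2.9. With 33 evaluable patients per arm: 0.075 × 33 = 2.5.

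**Break-even.** The documents give no rate of admission for RT complications, so a range is assumed. If q is the uncounted rate per Arm 2 patient, the full ratio is (0.075 + q)/0.150, while the recorded ratio stays at 0.50:

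| q (assumed) | Arm 2 admissions per 37, all | Full ratio |
|---|---|---|
| 0.02 | 3.5 | 0.63 |
| 0.05 | 4.6 | 0.83 |
| 0.075 | 5.6 | 1.00 |
| 0.10 | 6.5 | 1.17 |
| 0.15 | 8.3 | 1.50 |

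Equality is reached at q = 0.075, or 0.075 × 37 ≈ 2.8 admissions. Three such admissions are 3/37 = 8% of the arm.

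**Effect on the test.** Poisson counts were simulated with 37 per arm, a two-sided 0.05 Wilcoxon test and 3,000 runs. With an equal true mean of 0.15 in both arms, rejection is 4.7% when all admissions are counted, 7.8% when 25% of Arm 2's are missed and 17.2% when 50% are missed. At a true mean of 0.30 the last two become 8.8% and 24.9%. The missed shares are assumptions. Under the plan's own rates (0.150 v 0.075) the test has about 18% power.

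**The case against.** The strongest reply is that the SRE definition is identical in both arms, that SRE-related admission is the stated objective, and that toxicity is a separate objective with its own reporting. Much of this stands.

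- *Pain admissions.* A reader might infer that pain admissions are also counted differently by arm. The documents do not support that. A pain admission leading to RT or surgery counts in either arm, and one without an SRE counts in neither. A difference would arise only through pain flare after upfront RT, or if irradiated lesions were re-treated less often, which the documents do not quantify.
- *The registry.* Section 3.0 reports of inpatients seen for symptomatic bone metastases: "Among these patients, two-thirds went on to receive RT for pain management". It is tempting to treat the remaining third as an Arm 2 undercount. The registry has no arms. Applied to both, equal rates of 0.15 become 0.15 × 2/3 = 0.10 in each, with no spurious difference. Section 14.0 also gives a different share, 75%.
- *Infection after surgery.* Section 11.0 warns: "If surgery is needed on the radiated bone, patient can also be at higher risk for infection". That is not an example of an omitted admission, since orthopedic surgery to bone is itself an SRE in either arm. Rib and vertebral fractures listed as RT toxicities may likewise be recorded as SREs and count against Arm 2.
- *Hidden harm.* Arm 2 toxicity admissions are not invisible. Section 11.1 requires reporting of adverse events after the first RT dose, and Section 17.2 makes an adverse event that leads to admission serious. What is missing is an equivalent for Arm 1. The general wording of Section 11.1 and the optional assessment at an SRE could be read as reaching Arm 1, but Section 10.0 excludes Arm 1 from the scheduled evaluations.
- *Direction.* Section 13.0 keeps patients on protocol until 12 months or an SRE. If follow-up stops at an SRE, later admissions are lost more often in the arm with more SREs, which acts against upfront RT's advantage. On that reading, complications of on-demand RT would also be lost. This is a second defect in the same count, not a cure for the first.

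The reply does not meet the core: admissions caused by the intervention fall outside the only planned comparison, and nothing arm-neutral stands beside it.

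**Conclusion.** The point holds in a limited form. Admissions for complications of upfront RT are by implication excluded from the hospitalization comparison, while complications of on-demand RT can be attributed to an SRE. The likely effect favours upfront RT, and the cost surrogate is incomplete. Because relatedness is undefined, the text shows an open attribution rule with a probable direction, not a bias fixed by definition.

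The size is unknown. The expected benefit is small, about 2.8 admissions per 37 patients under the assumptions above, so about three uncounted Arm 2 admissions would be enough to offset it. That number is a break-even, not an estimate; Section 14.0 itself expects RT not to add toxicity. This is a secondary endpoint with low power, and the primary analysis is untouched. The improvement is cheap and worth making.

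**What to change.** Keep the SRE-related count as the stated objective. In Sections 12.2 and 14.0:

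- Add between-arm comparisons, in number and days between randomization and the earlier of death and 12 months, of (a) all-cause admissions and (b) admissions for bone-metastasis pain or complications, or for complications of any RT. Abstract both identically in the two arms, whether or not an SRE is recorded.
- State whether complications of on-demand and of upfront RT count as SRE-related.
- Report RT courses per patient by arm, upfront plus later, with the cost surrogate.
- Reconcile the Section 13.0 rule on remaining on protocol until an SRE with the 12-month window in Section 14.0, so that admissions after a first SRE are counted.

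The cost is protocol and SAP wording and modest extra chart abstraction for 74 patients. The broader counts will be noisier than the SRE-related count. That is a reason to report them alongside it; replacing the stated endpoint would be a trade-off that this point does not require.

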#### 13.0 CRITERIA FOR REMOVAL FROM STUDY

Patients will be removed from the study if any of the following criteria are met, after review by the principal investigator:

- 1. A change in the patient's medical status unrelated to RT results in the patient being unable to comply with the protocol.
- 2. Patient is unable to continue follow-up as outlined within the protocol
- 3. Patient is found to be ineligible based on the criteria in section 6.0 of this protocol.
- 4. Patient requests to withdraw from the protocol.
- 5. Patient death.

Otherwise, patients will continue on protocol until 12 months have elapsed since date of randomization or until an SRE occurs.

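### The count of SRE-related admissions mixes admission rate with survival time, and the plan contradicts itself on whether counting continues after a first SRE

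*Combined protocol and SAP*

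**What the plan says.** Section 14.0 states the aim as "To compare the number of hospitalizations related to SREs between standard of care and upfront, early palliative RT arms", and the method as "we will employ a Wilcoxon rank sum test". The unit is the patient: "Secondary objectives will be analyzed per patient". Unless stated otherwise, "all endpoints are defined within the time window from the date of randomization to death or 12 months, whichever occurs first". The same section expects incomplete follow-up: "We expect 60-80% of the enrolled patients can be followed for 1 year".

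For this endpoint, Sections 12.2 and 14.0 give no rate, offset, recurrent-event method or handling of death as a competing event. They also give no rule for patients who leave early.

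Section 13.0 says that, apart from the listed reasons for removal, "patients will continue on protocol until 12 months have elapsed since date of randomization or until an SRE occurs". Section 14.0 describes the primary analysis as lesion-based, "so an SRE (or no SRE) at one site does not affect the status of other sites from the same patient".

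**The concern.** A rank test on raw counts treats a patient who dies in month 1 without an admission the same as one followed for 12 months without an admission. If survival differs between arms, the arm with less time at risk collects fewer admissions even at the same admission rate. The shift can go either way: if upfront RT lengthened survival, RT patients would have more time in which to be admitted.

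The Section 13.0 rule adds a second problem. Read literally, it stops observation at the type of event that produces the admissions being counted, and it does so sooner in the arm with more SREs.

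This is the first-listed secondary objective, and it supports the health-resource argument in the Hospitalization part of Section 3.0. A p-value from the Wilcoxon test alone would not tell a reader whether a difference reflects admissions or survival, and it gives no effect size.

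**Working it through.** **Stated figure.** The plan gives no size or power for hospitalizations. Its only figure is for the primary endpoint: 60% v 30%, one-sided alpha 0.05, power 80%.
- n per arm = [1.645·√(2·0.45·0.55) + 0.842·√(0.24 + 0.21)]² / 0.30² ≈ 33, so 66 in total, and 66/0.90 = 73.3, rounded up to 74. This reproduces the plan.
- 74/2 = 37 per arm is used below.

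**Inputs from the documents.** One-year SRE rate 60% v 30% (Section 14.0); 25% of SREs admitted (Section 3.0, Hospitalization; a second study there gives 26%); 60-80% followed for 1 year (Section 14.0).

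**Assumptions.** Exponential death and SRE times; the 60% and 30% read as per-patient one-year risks; follow-up read as survival; two-sided 5% Wilcoxon test, since no level or sidedness is stated for this endpoint. The 60% v 80% split between arms is a stress contrast, because the plan gives that range for all patients together.

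**1. Admission rate.** SRE hazard −ln(0.40) = 0.916 per year; × 0.25 = 0.229 admissions per patient-year.

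**2. Mean time at risk within 12 months.** With one-year survival S this is (1 − S)/(−ln S).
- 60%: 0.40/0.511 = 0.783 years.
- 80%: 0.20/0.223 = 0.896 years.

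**3. Mean count at an equal rate.** 0.229 × 0.783 = 0.179 v 0.229 × 0.896 = 0.205. The ratio is 0.783/0.896 = 0.87, or 13% fewer admissions in the arm with more deaths. Dividing each count by time at risk returns about 0.23 in both arms, a rate ratio of 1.00.

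**4. Error rate (4,000 simulated trials, 37 per arm).**

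| Setting, equal true rates | Rejects | Favours arm with more deaths |
|---|---|---|
| 70% v 70% survival, 0.229/yr | 4.6% | 2.5% (either arm) |
| 60% v 80%, 0.229/yr | 5.7% | 4.3% |
| 60% v 80%, every SRE admitted (0.916/yr) | 8.3% | 7.4% |

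Repeat runs of the second row gave 5.2-5.7% rejection and 4.2-4.8% favouring the arm with more deaths. With 65% v 75% survival at 0.229/yr, rejection was 5.6%.

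**5. If observation stops at the first SRE.** Take 70% one-year survival in both arms (death hazard 0.357) and 25% of SREs admitted in both. The RT-arm SRE hazard is −ln(0.70) = 0.357.
- Full window: mean time (1 − 0.70)/0.357 = 0.841 years. Counts are 0.229 × 0.841 = 0.193 v 0.089 × 0.841 = 0.075, ratio about 2.6.
- Stopped at first SRE: mean time (1 − e^−(λ+μ))/(λ+μ), with λ the SRE hazard and μ the death hazard, gives 0.566 v 0.715 years (6.8 v 8.6 months). Counts are 0.229 × 0.566 = 0.130 v 0.089 × 0.715 = 0.064, ratio about 2.0.
- Simulated power falls from 26-27% to 16-17%. The standard-of-care arm still has the higher count.

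**6. Sections side by side.** Section 14.0 counts secondary endpoints to death or 12 months and says one site's SRE leaves other sites unaffected. Section 10.0 schedules all patients at 3, 6 and 12 months. Section 13.0 ends time on protocol at an SRE. These cannot all govern data collection.

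**The case against.** The strongest reply is that the objective is worded as a number of hospitalizations and that Section 12.2 presents it as a surrogate of cost. Admissions accrued to death or 12 months are a legitimate burden measure, and a person-time rate answers a different question. This stands, and it is why the Wilcoxon test should stay. What is missing is a statement of that choice and an instruction to read the result with survival.

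Section 14.0 also considers earlier deaths from RT extremely unlikely, and overall survival is tested separately. That makes an imbalance visible, but it does not exclude a survival benefit or a chance difference with 37 per arm.

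A reader might infer two stronger claims that the documents do not support:
- **Serious type I inflation.** Rejection rates of 8.7% (60% v 80% survival) and 20.6% (40% v 80%) arise at 1 admission per patient-year, about four times the rate the documents imply and without a source in them. The 40% figure also lies outside the stated follow-up range.
- **Removal at an SRE makes the arm with more SREs look better.** That needs equal admission rates despite 60% v 30% SREs, so SREs in the RT arm would have to lead to admission about 0.916/0.357 = 2.6 times as often. Nothing in the documents suggests this. With the same admitted share in both arms, the contrast shrinks but does not reverse.

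Finally, the Section 13.0 sentence may refer only to protocol visits. If so, no admissions are lost and only the wording needs correcting.

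**Conclusion.** The concern holds at a modest size; severity is minor to moderate. The planned comparison mixes admission rate with survival time. At the documents' inputs and an assumed 60% v 80% survival contrast, the Wilcoxon test's overall error rate stays near 5%. The distortion is in the comparison itself: about 13% fewer admissions in the arm with more deaths at an equal rate, and about 4% rather than 2.5% of trials falsely favouring that arm. A smaller survival difference gives a smaller effect; a higher admission rate gives a larger one.

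The contradiction between Sections 13.0 and 14.0 is a separate defect. If Section 13.0 governs data collection, SRE admissions after the first SRE are lost, more so in the arm with more SREs. The expected count ratio then falls from about 2.6 to 2.0 and power from about 27% to 17%, which works against the trial's own hypothesis. This rests on 70% survival and 25% of SREs admitted in both arms.

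**What to change.** 1. Reconcile Section 13.0 with Section 14.0 so that SRE-related admissions are counted to death or 12 months in every patient, including after a first SRE. State how patients who leave early contribute. This concerns data collection only.
2. Add an admission-rate comparison: Poisson regression with robust variance, or negative binomial, with log time at risk as offset. Report the rate ratio with its confidence interval.
3. Keep the Wilcoxon test on counts, labelled as the burden measure, and present both results alongside overall survival.

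The cost is protocol and SAP wording, plus continued capture of admissions after an SRE if Section 13.0 is now applied literally. The rate needs a count and an end-of-observation date per patient; Section 12.2 already provides for the number of hospitalizations, and overall survival needs death dates.

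The downside is sparse data. At 70% survival the expected admissions are 37 × 0.193 ≈ 7 in the standard-of-care arm and 37 × 0.075 ≈ 3 in the RT arm, so the interval will be wide. With about 7 admissions per arm, the robust Poisson test rejected in about 3.4-4.3% of null trials, so it is slightly conservative. The rate also treats death simply as the end of time at risk, which is a further reason to report it beside the count and survival.

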# 4.2.3 Brief Pain Inventory Short Form

Patients enrolled on either arm will undergo assessment of patient reported cancerspecific pain questionnaire using the Brief Pain Inventory Short Form at baseline, 3 months, 6 months, 12 months and optionally but recommended within one week of any SRE (Appendix, ~5 minutes to complete). For patients randomized to receive upfront, early RT, they will complete the form once every 5 treatment days during RT. The Brief Pain Inventory is a validated method in rapidly assessing the severity of pain and its impact on functioning. It is a 9 item self-administered questionnaire used to evaluate the severity of a patient's pain and the impact of this pain on the patient's daily functioning. Patients are asked to rate their worst, least, average, and current pain intensity, list current treatments and their perceived effectiveness, and rate the degree that pain interferes with general activity, mood, walking ability, normal work, relations with other persons, sleep, and enjoyment of life on a 10 point scale. Patients will be able to rate their pain on a 0 to 10 scale, 0 being no pain and 10 being the worst pain, for different time points (within the last 24 hours, on average, at the time of filling out the form). Patients will also be asked what treatments or medications they are receiving for pain from their understanding, and how much relief they received from the pain treatment and medications (0% being no relief and 100% being complete relief). Patients will also evaluate how much the pain has interfered with their activities and function (0 being does not interfere and 10 being completely interferes).

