sum tests and established minimally important differences (MIDs) for the various measures, respectively. For scale scores with no established MIDs, the "half standard deviation" rule will be applied (i.e., differences of a half standard deviation will be considered clinically significant). At the conclusion of the study data at each time point will be presented, the number of patients in each group at a given time point will be documented, and the mean EQ-5D-5L and BPI scores for each group will be plotted over time and longitudinal pattern will be examined with the possibility of proposing more complicated regression methods such as the linear mixed models. The categorical answers (e.g., YES vs NO) from EQ-5D-5L will be compared between the two arms using Fisher"s test at each time point as well and odds ratios together with confidence intervals will be computed. Other non-quantifiable answers (e.g., treatment receiving for pain) will be summarized descriptively. For the last question in BPI, the score for pain interference on the BPI Short Form is the mean of the 7 interference questions as long as at least 4 are completed.

For comparing pain-free survival and overall survival between the two arms, both of which are time to event endpoint (time from randomization to start of opioids or death which is not necessarily within 12 months from randomization), we will use log-rank test.

To evaluate CTCAE v4 toxicity events in the upfront RT arms, we will tabulate all toxicities and summarize the CTCAE v4.03 scores and present descriptive statistics. This will be done at 3 months, 6 months, and 12 months from randomization.

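### Section 14 answers the pain quality-of-life objective with about 15-18 unadjusted BPI tests (36-39 with EQ-5D-5L) and no lead score or visit, and judges clinical significance without regard to precision

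*Combined protocol and SAP*

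**What the plan says.** Section 2.0 has a secondary objective to compare pain-related quality of life between arms using the BPI. A separate objective is to collect health utilities with EQ-5D-5L.

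Section 14.0 tests the questionnaire results between arms at "3 months, 6 months, 12 months and optionally but recommended within one week of any SRE". The scores are described as "The individual quantitative scores derived from the BPI, and the utility scores as well as the overall health scores derived from EQ-5D-5L". On how differences are judged, it says "quantitative scores at various time points of interest will be evaluated for both statistical and clinical significance using Wilcoxon rank" sum tests for the first and established MIDs for the second. Only where a scale has no established MID does a fallback apply: "differences of a half standard deviation will be considered clinically significant". Categorical EQ-5D-5L answers get Fisher's test at each time point, with odds ratios and confidence intervals.

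Section 4.2.3 shows what the BPI yields: "Patients are asked to rate their worst, least, average, and current pain intensity", plus a percentage for pain relief and the interference items. For the last group, Section 14.0 gives a scoring rule: "the score for pain interference on the BPI Short Form is the mean of the 7 interference questions", provided at least four are completed.

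For these tests Section 14.0 names no lead score, lead visit, alpha, sidedness or multiplicity adjustment. The one alpha it states, one-sided 0.05, belongs to the primary SRE test. Linear mixed models are mentioned only as a possibility.

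**The concern.** The pain objective is a single question, but the plan gives it many answers and does not say which one counts. Once the data are seen, any score at any visit could be put forward as the quality-of-life result. The clinical reading adds a second route to a claim: it compares an observed difference with a threshold, ignores that difference's standard error, and is not stated to depend on the statistical test. Section 3.0 offers better pain-free survival and quality of life as a rationale for early RT in patients with few or no symptoms. A chance pain difference could therefore be read as support for the treatment.

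**Working it through.** **The plan's own figure.** Section 14.0 gives no size or error calculation for the questionnaires. Its one calculation is for the primary endpoint: 60% vs 30%, one-sided 0.05, 80% power. With n = [1.645·√(2·0.45·0.55) + 0.8416·√(0.24 + 0.21)]² / 0.30² = 1.722²/0.09 = 32.9, this gives 33 per arm, or 66. Allowing 10% withdrawal, 66/0.9 = 73.3, so 74. These figures reproduce, and nothing below alters them.

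**Number of tests.**
- BPI: 4 intensities (Section 4.2.3) + 1 interference mean (Section 14.0) = 5 scores, or 6 if the relief percentage is counted. Over 3 fixed visits: 15 or 18 tests.
- EQ-5D-5L: 2 quantitative scores, namely "the utility scores as well as the overall health scores derived from EQ-5D-5L", + 5 dimensions (Section 4.2.4) = 7. Over 3 visits: 21 tests.
- Total: 15 + 21 = 36, or 18 + 21 = 39. The optional SRE-triggered assessment would make it 13 × 4 = 52; it is left out here.

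**Chance of at least one p<0.05 with no true effect.** Assumptions: two-sided 5% per test; correlation between scores and between visits as shown; multivariate-normal test statistics.

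| Tests | Expected false positives | Independent, 1 − 0.95^k | Correlation 0.5 scores, 0.4 visits | 0.7, 0.5 | 0.8, 0.6 |
|---|---|---|---|---|---|
| 15 (BPI, no relief) | 0.75 | 54% | 43% | 34% | 28% |
| 18 (BPI) | 0.90 | 60% | 47% | 37% | 30% |
| 36 | 1.80 | 84% | 65% | 49% | 39% |
| 39 | 1.95 | 86% | 67% | 51% | 40% |

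The independent column is an upper-end figure, since these scores are correlated. As a cross-check, a simulation that ran the Wilcoxon and Fisher tests themselves (33 per arm, each EQ-5D-5L item cut into two categories at the median) gave 66%, 50% and 39% for all 39 tests. There the correlations between scores and between visits were both 0.5, both 0.7 and both 0.8.

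**The half-SD reading.** Section 14.0 expects 60-80% of patients to be followed for one year: 0.6 × 37 = 22.2 and 0.8 × 37 = 29.6, so about 22-30 per arm. In SD units, SE = √(2/n). The 95% CI half-width is 1.96·SE, and the chance that an observed difference reaches 0.5 SD in either direction with no true effect is 2·[1 − Φ(0.5/SE)].

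| n per arm | SE | CI half-width | Chance of ≥0.5 SD under no effect |
|---|---|---|---|
| 22 | 0.302 | 0.59 SD | 9.7% |
| 30 | 0.258 | 0.51 SD | 5.3% |
| 33 | 0.246 | 0.48 SD | 4.2% |

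At 22-30 per arm the half-width exceeds 0.5 SD, so an observed half-SD difference has a 95% CI that includes zero.

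**The case against.** Several stronger readings are tempting, and the documents do not support them.

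- **That any half-SD difference counts as clinically significant.** It does not. Established MIDs come first, and half an SD applies only to scores without one. The plan does not say which scores those are, so the reach of the fallback is unknown.
- **That a clinical claim would rest on no test at all.** Every quantitative score also gets a Wilcoxon test. The gap is narrower: the plan does not say that both conditions must be met. Requiring both would help only in part. With no true effect, 33 per arm and half an SD applied to all eight quantitative scores, at least one of the 24 score-by-visit comparisons met both in 24-45% of simulated trials (correlations 0.8 down to 0.5).
- **That 39 tests is a floor and all bear on pain.** The count is inferred, and it is 36 without the relief item. The pain objective is tied to the BPI alone, so its own burden is 15-18 tests.
- **That the rule is faulty because a true half-SD effect is missed half the time.** An unbiased estimate of an effect equal to the threshold falls short about half the time at any sample size.

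It is also fair to say that a 5-10% chance trigger is not far from an ordinary 5% test, and that at 33 per arm it is slightly stricter. The plan also commits to presenting data at every time point with numbers per group and to plotting mean scores over time. That makes selective emphasis easier to see. It does not control error or say which result answers the objective. The absence of a lead comparison and of a precision condition stands.

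**Conclusion.** The point holds in this form. A secondary objective is tested 15-18 times with nothing named as decisive, which gives roughly a 28-47% chance of at least one nominally significant BPI result when there is no effect, and 40-67% over all 39 questionnaire tests. Alongside this, clinical significance can be read from a point estimate that, at the implied 12-month numbers, cannot be told apart from zero when it sits at half an SD.

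The percentages rest on a two-sided 5% level, which the plan does not state, and on assumed correlations of 0.5-0.8 between scores and 0.4-0.6 between visits. The 22-30 per arm assumes that everyone followed to one year returns the forms; the protocol gives no return rate. No correlation examined brings the chance near 5%.

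A reader might infer that the trial's main conclusion is at risk. It is not: the primary SRE analysis and its sample size are untouched. The change should be made, but it concerns secondary endpoints only.

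**What to change.** Before any data are seen, amend Section 14.0 to:

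1. Name one lead comparison for the pain objective, tested at two-sided 5%. This can be one BPI score at one visit, or one between-arm contrast from a mixed model across visits. The choice belongs to the investigators. Pain interference is one candidate, because its scoring rule is already written.
2. Label all other BPI and EQ-5D-5L comparisons exploratory, and report them as between-arm differences with 95% CIs.
3. List the MID to be used for each score, and state which scores fall back to half an SD.
4. Interpret each difference by where its CI lies relative to zero and to the MID, not by the point estimate alone. The lead test should not decide clinical importance for every other score.

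The cost is SAP wording only: no added patients, visits or forms. The downside is that the remaining questionnaire comparisons become descriptive.
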